## I. BACKGROUND

Allogenic hematopoietic stem cell transplantation (HSCT) is used frequently for treating hematologic malignancies [1]. Graft-versus-host disease (GVHD) is one of the major complications of HSCT [2,3] and the main cause for transplant-related morbidity and mortality. GVHD has been divided into acute and chronic with distinct clinical manifestations. Manifestations of acute GVHD include maculopapular skin rash, nausea, vomiting, diarrhea and cholestatic jaundice.

The median occurrence for significant acute GVHD (grade II-IV) is about 40%. Moderate to severe acute GVHD occurs in up to 30% of patients despite receiving cells from a fully matched human leukocyte antigen (HLA) related or unrelated donor and immunosuppressive therapy [4,5,6]. Chronic GVHD is a common late challenge associated with HSCT. Roughly 50% of the patients experience some degree of chronic GVHD ranging from 30 to 80%. Chronic GVHD is a leading cause of late nonrelapse related mortality

With such impact of GVHD on morbidity and mortality, effective prophylaxis of GVHD is quite important. A common approach for such prevention includes prophylactic use of a regimen with immunosuppressive agents given after HSCT. Corticosteroids (typically methylprednisolone or prednisone) are the standard therapy for patients with acute GVHD grade II-IV. The starting dose of steroids are generally 2mg/kg for all patients with grade II-IV acute GVHD except for isolated upper GI GVHD wherein 1mg/kg is commonly the starting dose. High dose corticosteroids are employed as a front line agent to treat this complication [5, 6, 7, 8]. High dose steroid therapy is associated with a variety of adverse side effects including avascular necrosis, cataracts, edema, gastritis, headaches, hyperglycemia, hypertension, hypokalemia, insomnia, infections, mood swings and steroid myopathy [9].

Steroid myopathy is the most significant complication of such corticosteroid therapy [8, 10]. Once patients become impaired with significant loss in functional status; outcomes are poor with marked increase risk of infections. Incidence rate of such myopathy has been estimated at least at 41% [10]. Although the presentation can be acute, most often it is insidious.

To date, research has been infrequent in this common complication of GVHD therapy. The only study to address this complication came from our institution [10] in the form of a retrospective review of 180 patients. Seventy of these patients met inclusion criteria. Twenty nine of these patients were evaluated by physical therapists with manual muscle exam (MME) and for functional independence measure (FIM) scores. With MME data missing for 3 patients, 11 patients had scores of 3 out of 5 with MME (movement in full range of motion against gravity without resistance) in upper extremities. Thirteen patients had scores of 3 in lower extremities. These scores constituted myopathy from functional perspective. In 11 and 13 patients, scores of 4 out of 5 with MME (movement against moderate resistance) were noted with upper and lower extremities respectively. Patients with such strength may be able to ambulate and transfer independently but such independence is not guaranteed. The majority of the patients needed assistance with device(s). They also needed some degree of assistance when performing tasks including supine to sit transfer (17 out of 29), sit to stand transfer (18 out of 29), and walking (22 out of 29). This study was limited by being retrospective with likely only the severe cases referred for evaluation.

To date, despite being a common complication across many different diseases which necessitate high-dose steroid treatment, there is no formal definition or disease-severity index for patients with steroid myopathy. A major area of acute GVHD research is to develop therapies which minimize exposure to corticosteroids. These therapies may result in comparable GVHD response rates yet are ultimately preferable because of reduction in toxicity. Being able to quantify protection from steroid-myopathy is integral to interpreting these studies. The goal of this protocol is to perform a prospective pilot study to define steroid myopathy (definition, measures, incidence, severity) and impact on non-relapse mortality in a homogenous population of patients with newly diagnosed acute GVHD.

There are very limited studies and limited knowledge of the weakness and subsequent functional deficits that develop in patients with steroid myopathy. There are no formal tools used to identify or quantify impairments in patients suspected of having steroid myopathy. Steroid myopathy usually affects proximal musculature with preferential involvement of lower extremities, especially quadriceps [11]. With such weakness, significant functional sequelae include among others, inability to independently sit from supine position (only 31%) and stand from sitting position (28%) [10].

The diagnosis of steroid myopathy in HSCT patients was previously based on Manual Muscle Exam (MME) and Functional Independence Measure (FIM) [10]. However, manual muscle testing is examiner-dependent and can be non-specific. Tests such as the Peripheral Motor Deficits Scale (PMDS), Stepper test, and Ankle/Wrist index and Neuropathy Disability Score [12] have been used; however, these tools have not been validated and are rarely utilized in clinical or research settings. Laboratory and imaging tests cannot reliably diagnose steroid myopathy. Electromyography is an invasive test which cannot be used solely to make such a diagnosis as some of the findings may be non-specific. In addition, it may be too invasive in this setting of patients who have just received a stem cell transplant. The Adult Myopathy Assessment Tool (AMAT) has been used in patients with inflammatory myopathies, spinal and bulbar muscular atrophy [13], but has not been specifically utilized for steroid myopathy. This

assessment includes 7 timed functional tasks and 6 endurance tasks, has high interrater and intra-rater reliability and correlation with other physical assessments such gait speed, and the physical quality of life. The Brooke scale was developed to assess upper extremity functional performance in Duchenne Muscular Dystrophy patients and is easy to apply and interpret [14, 15]. It has also been applied in the rehabilitation setting for patients with spinal muscular atrophy [16] Again, none of these tests have been studied in patients with steroid myopathy.

No known therapy exists to prevent or to enhance recovery after the development of steroid induced myopathy, although rehabilitation measures may improve outcomes of these patients [17, 18]. Engaging in treatment for patients who develop steroid myopathy is not possible because the not much is known about the time course of the weakness that develops. There are no known tools to assess and measure the weakness; and thus, putting together a treatment regimen or even pursing a prospective study to implement an intervention becomes a challenge. A major objective of this research is to identify the best tools to capture steroid myopathy incidence and severity. An ideal tool should be: 1) easy to perform and measure by multiple disciplines, 2) easy to interpret the results, 3) be able to discern post-transplant disability from steroid myopathy, and 4) may be used with patients with varying severity of weakness.

Because there are limited diagnostic tools available to formulate a diagnosis of steroid myopathy, it is important to study the functional and physical changes that may occur if a patient develops steroid myopathy. It is important to use measures that are widely utilized in the literature such as the 6 minute walk test, 5 times sit-to-stand, and manual muscle testing, along as ones such as the AMAT and Brooke Scales, which have been used in other myopathy settings. Based on the patterns of physical and functional decline measured in this study, we can formulate surrogate markers that will be essential in conducting future prospective interventional studies in patients who have been diagnosed with or are at risk for developing steroid myopathy.

# **II. OBJECTIVES**

#### **Primary Objective:**

1. To perform a pilot study to estimate the change in six physical and functional tests over time in patients with suspected acute graft-versus-host disease (GVHD) who have been initiated on treatment with corticosteroids.

#### Secondary Objectives:

1. To describe and potentially define steroid myopathy by following the patterns of the muscle loss and functional impairment in this population of patients.

2. To follow steroid myopathy and describe its incidence, its severity, and the impact on non-relapse mortality in a homogeneous population of patients with suspected acute graft-versus-host disease (GVHD) who have been initiated on treatment with corticosteroids at a quaternary institution in the inpatient and outpatient setting.

3. To estimate the adherence to an intermittently supervised exercise program in hematopoietic stem cell transplantation (HSCT) patients who are at risk of developing steroid myopathy.

**Hypothesis** – There will be a decline in muscle strength and functional measurements in patients with suspected graft versus host disease who have been started on corticosteroids which will be detected at the Day 28 follow up, and may be more robust at the Day 56 follow up. Steroid myopathy and steroid-myopathy severity is correlated with non-relapse mortality in patients with newly diagnosed acute GVHD.

# **III. STUDY ENDPOINTS:**

# **Primary Endpoints:**

• Physical and functional measurements and the changes in these measures over time.

# Secondary Endpoints:

- Physical and occupational therapy is often prescribed for patients who develop steroid myopathy. It is unclear how many adhere to their exercise regimens. We will estimate the adherence to the study exercise program, tolerance for specific exercises and ability to advance exercises, and completion of study materials.
- We will also measure the percentage of patients who agree to participate in the study as this information will provide us with an estimate of the percentage of patients who may participate for future studies and measures.
- Patient self-reported outcomes in functional status and symptoms over time while being followed for GVHD.
- Overall status of disease and survival at day 180. This includes assessing the impact on non-relapse mortality at 6 months post-enrollment.
- We will assess other variables (age, gender, co-morbidities, type of graft, etc.) that may impact incidence of steroid myopathy in this group of patients.
- Changes in physical and functional measurements in comparison to their cumulative steroid dosing.
- Changes in physical and functional measurements in comparison to the severity of GVHD.

# IV. ELIGIBILITY CRITERIA:

# Inclusion:

- 1) Participants are willing and able to give written informed consent and to comply with all of the study visits and procedures.
- 2) Age  $\geq$  55years, or with a Sorror co-morbidity index of  $\geq$  3 ]
- 3) Post allogenic hematopoietic stem cell transplantation using bone marrow, peripheral blood or cord blood; or after pre planned donor lymphocyte infusion.

- Presumptive diagnosis of acute GVHD necessitating high-dose corticosteroid treatment (with an approximate starting dose of methylprednisolone equivalent of 2mg/kg/day).
- 5) Within 5 days of receiving corticosteroid treatment
- 6) ECOG (Eastern Cooperative Oncology Group) performance status of 0, 1, or 2 or equivalent Karnofsky score of 60 or higher.
- 7) The patient is referred to the study by their stem cell transplant attending physician.

# Exclusion:

- 1) Non-English speaking
- 2) Patients under 18 years of age
- 3) Underlying unstable cardiac or pulmonary disease in the opinion of the investigator that limits participant involvement in exercise.
- 4) Has a pre-transplant echocardiogram with ejection fraction <45%.
- 5) Requires supplemental oxygen to maintain O2 saturation >92%
- 6) Musculoskeletal injury that precludes participation in an exercise program
- 7) Inability to participate in a structured exercise program
- 8) Patients for whom the physician feels is unsafe for an exercise program
- 9) Platelets equal to or less than 10,000 or evidence of active bleeding
- 10)Patients who are unable to understand or follow through with the exercise program

# V. STUDY PLAN

Given the pattern of weakness associated with steroid myopathy, we will measure the following:

a) Objective Functional/physical measures:

# a. Manual muscle testing

- i. Measure strength of shoulder abduction, elbow flexion, extension, hip flexion, and quadriceps bilaterally.
- ii. Cumulative score out of 50 points total.
- b. Hip flexor and quadriceps strength via handheld dynamometer
  - i. Reported as strength in pounds
- c. Six minute walk test
  - i. Reported as meters
- d. 5x sit to stand
  - i. Reported as total time in seconds
- e. Brooke Scale:
  - i. Reported as numerically as 1-6.
    - 1. From arms at side, abduction of arms in full circle until touching overhead
    - 2. Can raise arms above head only flexing the elbow or using accessory muscles

- 3. Cannot raise hands above head, but can raise an 8 ounce glass of water to the mouth
- 4. Can raise hands to the mouth, but cannot raise an 8 ounce glass of water to the mouth
- 5. Cannot raise hands to the mouth, but can use hands to hold a pen or pick up pennies from the table
- 6. Cannot raise hands to the mouth and has no useful function of hands
- f. Adult Myopathy Assessment Tool (AMAT) Only portion of the test will be administered:
  - i. Reported as summation of the tasks below (total 24 points).
    - 1. Arm raise (0-3)
    - 2. Sustained arm raise (0-4)
    - 3. Sit to stand (0-3)
    - 4. Sustained hip flexion (0-4)
    - 5. Sustained knee extension (0-4)
- b) Subjective/Patient reported
  - a. Self reported Improved (or PROMIS) Health Assessment Questionnaire
  - b. PROMIS Short Form v1.0 Physical Function 12a.
  - c. MD Anderson Symptom Inventory (MDASI)
  - d. FACIT-Fatigue Scale

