#### c) Baseline demographics

- a. Pre-transplant comorbidity index (Sorror)
- b. Underlying disease requiring transplantation
- c. Disease stage at the time of transplant
- d. Donor type
- e. Graft Source
- d) GVHD-associated measurements at baseline and after initiation of corticosteroids at Day 14(+/-5), 28 (+/-5), and 56 (+/-5)
  - a. Organ Stage and Grade of GVHD (see Table 1)
  - b. Corticosteroid dose at that time and cumulative corticosteroid dose through day 56.
    - Doses of methylprednisolone will be converted to prednisone equivalents by multiplying the methylprednisolone dose by 1.25. Prednisone doses for each subject will be converted to mg/kg. The cumulative and average corticosteroid doses will be calculated over time.
  - c. GVHD Response (at days 14, 28, 56)
  - d. Body mass index (BMI), albumin, prealbumin levels. Albumin and possibly prealbumin levels are collected by the stem cell transplant team whether

the patient is on study or not (standard of care) and are not researchspecific procedures. Prealbumin levels will be recorded if they are obtained by the medical team.

- e) During the Day 180 post-transplant follow up:
  - a. Acute and chronic GVHD assessment, if patient is returning to MDACC
    - i. Grade of GVHD, GVHD response
  - b. Body mass index (BMI), albumin levels, will be collected from the medical record if available.
  - c. Non-Relapse Mortality: non-relapse mortality due to any cause other than the underlying malignancy, will be assessed at Day 180
  - d. Overall survival: Overall survival will be computed up to Day 180

With the exception of the baseline demographic information, physical/functional measures, patient reported questionnaires, and GVHD-associated measurements will be recorded at the following time points:

- a. Baseline (at the time of screening, consent and enrollment into the study)
- b. Day 14 (+/-5)
- c. Day 28 (+/-5)
- d. Day 56 (+/-5)

It will take approximately 15 minutes to perform the physical function tests and it will take approximately 20 minutes to complete the patient questionnaires during each patient evaluation session.

If a participant remains hospitalized as an inpatient, he or she will continue to participate in the exercise program allocated to them and the above measures will be recorded at the appropriate time intervals. The medical indication for hospitalization, discharge diagnoses and length of hospital stay will be recorded.

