# **VI. STATISTICS:**

The objective of this study is to estimate change in the six functional/physical measures (described in Section VI) over time. The information gained in this study will be used for future larger studies. These measures will be collected at baseline, two weeks, 4 weeks, and 8 weeks. Other secondary endpoints, such as patients' Self Reported Improved (or PROMIS) Health Assessment Questionnaire, PROMIS Short Form v1.0 – Physical Function 12a, MDASI, FACT-Fatigue, GVHD associated measures and corticosteroid dose will also be collected over the same time course. We plan to approach 70 patients (3 patients each month for an approximate period of 24 months of accrual). We expect that about 85% (60 patients) will agree to participate in the study. Further if 10 (20%) out of 60 patients drop out early due to developing significant weakness, disease progression, or have a prolonged and complicated inpatient hospital course, we expect 50 patients to complete the 8 week measures. With 50 patients, we will have an 80% power to detect an effect size of 0.404 in a functional measure change from baseline to 8 weeks using a paired t-test with a 0.05 two-sided significance level.

To explore the possible corticosteroid dose effect on the functional measures, graphical methods will be used to present data and the cumulative steroid exposure may be correlated with functional measures over time in a repeated measures analysis when appropriate. Furthermore, 2-week or 4-week cumulative steroid exposure may be compared between 6-month non-relapse deaths and others, provided patients all survive past 2 weeks or 4 weeks.

We expect about 20% non-relapse mortality rate at 6 months (NRM6). With about 10 non-relapse deaths, we will explore potential difference in baseline and/or the change of functional/physical measures between 6-month non-relapse deaths vs others. With 10 non-relapse deaths and 40 others, we will have an 80% power to detect an effect size of 1.011 in the difference of a functional measure at baseline between two groups using a two-sample t-test with a 0.05 two-sided significance level.

We will also evaluate adherence rates to the exercise regimen and drop-out rates/patterns, which is very important for the future larger study planning.

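### The baseline comparison of dynamometer strength between non-relapse deaths and others should adjust for sex, because force in pounds also reflects sex

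*Combined protocol and SAP*

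**What the plan says.** Section V (Study Plan, objective measures, item b) gives one scale for the handheld dynamometer: "Reported as strength in pounds". It names no sex-adjusted or weight-adjusted form.

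Section VI (Statistics) uses the functional measures in two ways.

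- **Within patients.** The sample size gives "an 80% power to detect an effect size of 0.404 in a functional measure change from baseline to 8 weeks using a paired t-test".
- **Between patients.** The plan will "explore potential difference in baseline and/or the change of functional/physical measures between 6-month non-relapse deaths vs others". The group sizes are given as "With 10 non-relapse deaths and 40 others", with "an 80% power to detect an effect size of 1.011 in the difference of a functional measure at baseline between two groups". The test named is a two-sample t-test at a two-sided 0.05 level, without covariates.

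Section III (Secondary Endpoints) lists gender among the variables that may affect the incidence of myopathy, but not as a covariate for strength. Section V, item d, records BMI and gives it no role in the analysis. The same item puts steroid dose on a weight scale: "Prednisone doses for each subject will be converted to mg/kg". The dose endpoint in Section III is "Changes in physical and functional measurements in comparison to their cumulative steroid dosing".

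**The concern.** A paired analysis compares each patient with himself or herself, so stable differences in force between men and women cancel. A comparison of baseline levels between two groups of different people has no such protection. Eligibility does not restrict sex, so the spread of baseline pounds contains a sex component as well as any weakness.

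Two consequences follow. First, the sex component adds to the SD against which the difference is judged, so a real difference in weakness is harder to see. Second, if sex is itself related to non-relapse death, part of the observed difference in pounds is a difference in sex mix.

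The comparison matters because Section II hypothesises a link between myopathy severity and non-relapse mortality, and Section I says the observed patterns will inform surrogate markers for later trials.

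**Working it through.** **1. Reproduce the plan's figures** (noncentral t, two-sided 0.05).

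- Two-sample, 10 vs 40: noncentrality = 1.011 / sqrt(1/10 + 1/40) = 1.011 / 0.3536 = 2.860, with 48 df. Power = 0.8001, and the difference solved for 80% power is 1.0109 SD. The stated figure is right.
- Paired, n = 50: noncentrality = 0.404 × sqrt(50) = 2.857, with 49 df. Power = 0.7996. The stated figure is right, and this point does not concern it.

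**2. Effect of adjusting for sex.** Let R² be the share of baseline force variance explained by sex. The residual SD is sqrt(1 − R²) of the total SD, and one covariate leaves 47 df. The documents give no strength SD, sex split or R², so R² is an assumption. This step takes sex as balanced between the groups.

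| R² (assumed) | sqrt(1 − R²) | Detectable difference, total SD | Power at 1.011 SD |
|---|---|---|---|
| 0 (unadjusted) | 1.000 | 1.011 | 80% |
| 0.1 | 0.949 | 0.96 | 84% |
| 0.2 | 0.894 | 0.90 | 88% |
| 0.3 | 0.837 | 0.85 | 92% |

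**3. Allow for chance imbalance.** With half of each sex, the difference in sex proportion between 10 and 40 patients has SD sqrt(0.25 × (1/10 + 1/40)) = 0.177, or 17.7 points. In simulation with sex unrelated to death:

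- For a sex gap of 0.5, 1.0 or 1.5 within-sex SD (assumption), the sex-adjusted model has about 81%, 87% and 93% power at 1.011 total SD. The gain survives chance imbalance.
- The unadjusted t-test rejects in about 5% of null trials in every case. On average, chance imbalance costs precision and does not inflate the error rate.

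**4. If sex is truly related to non-relapse death.** With a within-sex gap D and a real difference Δp in sex proportion between the groups, the bias in total SD is D × Δp / sqrt(1 + D²/4), taking half of each sex for the total SD.

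| D (assumed) | Δp = 0.20: bias; rejections with no true weakness difference | Δp = 0.30: bias; rejections |
|---|---|---|
| 0.5 | 0.10 SD; 6% | 0.15 SD; 7% |
| 1.0 | 0.18 SD; 8% | 0.27 SD; 12% |
| 1.5 | 0.24 SD; 11% | 0.36 SD; 18% |

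The documents do not show that sex is related to non-relapse death here, so this table is conditional.

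**5. Does the dose comparison share the problem?** The endpoint is defined on changes, so level differences cancel. What could remain is scaling: whether loss is proportional to starting strength.

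- Assume proportional loss: mean 20%, dose effect 0.06 per SD of dose, noise 0.10, baseline CV 30/40/50%. The correlation of loss with dose is 0.44/0.40/0.37 in pounds, against 0.06 / sqrt(0.06² + 0.10²) = 0.51 as a percentage.
- With loss fixed in pounds and the same parameters, the result reverses: 0.44/0.40/0.37 as a percentage, 0.51 in pounds.

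No statement in the documents decides between the two models.

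**The case against.** The strongest case against runs as follows. The unit line in Section V sits beside similar lines for metres and seconds, so it says how to record and not how to analyse. The t-test appears only in the power sentence, and Section VI also allows repeated-measures or GEE models, which can take covariates. Adjustment is therefore unspecified, not excluded. The issue touches one of six measures, in an exploratory comparison within a pilot. Every size above is assumed, and even the largest bias shown, 0.36 SD, is well below 1.011 SD.

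Most of this stands as a limit on scope. It does not remove the point: the only test named for this contrast is unadjusted, the improvement is specific, and stating it beforehand avoids choosing the model after seeing the results.

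A reader might infer more than the documents support:

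- **That the primary analysis is compromised.** It is paired, so it is not affected.
- **That chance sex imbalance with 10 deaths produces false positives.** Step 3 shows that the error rate stays at 5%.
- **That mg/kg dose set against pounds confounds the dose endpoint.** That endpoint is on changes, Section VI makes the repeated-measures analysis optional, and nothing shows that mg/kg dose varies with sex or size.
- **That percent change should be required.** Step 5 shows that the gain depends entirely on assuming proportional loss.
- **That weight adjustment should be mandatory.** Baseline falls within 5 days of steroid treatment, and Section I lists edema as a steroid effect. If weight already carries fluid or wasting related to death, adjusting for it can remove real signal.

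**Conclusion.** The point holds for one contrast: baseline dynamometer strength in non-relapse deaths compared with others. Under an assumed R² of 10-30%, the unadjusted test gives away about 0.05 to 0.16 SD of detectable difference (1.011 − 0.96 and 1.011 − 0.85), or about 4 to 12 points of power at 1.011 SD. Confounding arises only if sex is related to non-relapse death, which the documents neither show nor exclude. The stated power figures are correct. The finding does not extend to the paired analysis or to the steroid-dose comparison. It is a modest improvement at almost no cost.

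**What to change.** In Section VI, for the dynamometer measure only, replace the two-sample t-test of baseline strength (non-relapse deaths vs others) with a linear model of strength on group, adjusted for sex. Report as a sensitivity analysis a version that also adjusts for baseline body weight, and give the reason: weight at the start of steroids may already reflect edema or wasting.

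Keep pounds for recording and for the paired analysis. Leave the steroid-dose analysis as planned; showing change in both pounds and percent is optional.

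The cost is a sentence or two in Section VI and one degree of freedom (48 to 47), with a second in the sensitivity analysis. No new visits or patients are needed: gender is already named in Section III, and weight underlies the BMI and mg/kg values in Section V.

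### The 5x sit-to-stand has no recordable value for a patient too weak to finish it, so decline on this one of six primary measures would be understated

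*Combined protocol and SAP*

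**What the plan says.** The primary objective (Section II) is to "estimate the change in six physical and functional tests over time". Section V lists the six tests. Item d, the 5x sit to stand, has one output: "Reported as total time in seconds". The documents give no code for a failed attempt, no maximum time, no worst score, and no rule on arm use or help.

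The other five can register severe weakness. Manual muscle testing (out of 50), the Brooke scale (1-6) and the AMAT items (from 0) have scored worst categories, and the scales in pounds and metres allow a 0. One AMAT item grades sit to stand from 0 to 3.

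The hypothesis in Section II is directional: "There will be a decline in muscle strength and functional measurements in patients with suspected graft versus host disease". Section VI states that "we expect 50 patients to complete the 8 week measures" and that with 50 patients "we will have an 80% power to detect an effect size of 0.404", "using a paired t-test with a 0.05 two-sided significance level". It adds that repeated-measures or GEE models may be used to estimate change over time. It has no rule for missing or failed tests.

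The Background names loss of independent standing from a chair among the important consequences of this myopathy. It reports help needed with "sit to stand transfer (18 out of 29" patients in the institution's earlier series.

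**The concern.** Seconds cannot express failure. A patient who cannot rise five times has taken no finite time, and the natural entry is a blank. That blank is caused by the outcome being measured.

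The loss is also one-sided. The 5x sit-to-stand is part of screening, and enrolment requires ECOG 0-2 and the ability to exercise. Most patients should therefore have a baseline time, and inability should appear mainly at follow-up, among those who have weakened most. A comparison restricted to patients with two times leaves out part of the worst decline.

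At stake are the estimated change on one primary measure and the use of that estimate to plan the larger studies mentioned in Section VI. A test that becomes impossible as myopathy progresses could look insensitive only because its most informative results went unrecorded.

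**Working it through.** **1. The plan's own figure.** Section VI gives n = 50, effect size 0.404 (mean change / SD of change) and a two-sided 0.05 paired t-test. The noncentral t with 49 df and noncentrality 0.404 × √50 gives power 0.7996. The stated 80% reproduces.

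**2. Random loss, for comparison.** If patients without a time were a random subset, only sample size would suffer. At effect 0.404, power is 78.3% for n = 48, 75.5% for n = 45 and 70.3% for n = 40.

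**3. Loss linked to worsening.** Let change in seconds, in SD units, be normal with mean 0.404 and SD 1, positive meaning slower. A share q is unable, and ρ is the correlation between the tendency to be unable and the patient's own worsening. **Both q and ρ are assumptions; the documents give neither.** With c = Φ⁻¹(1 − q) and λ = φ(c)/(1 − q), patients with a time have:

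- mean change = 0.404 − ρλ
- SD = √(1 − ρ²(cλ + λ²))
- power from the noncentral t with n = 50(1 − q), rounded, and effect = mean / SD

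For q = 10%: c = 1.2816, φ(c) = 0.1755, λ = 0.1755/0.9 = 0.1950, cλ + λ² = 0.2879, n = 45.

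| ρ | mean change | SD | mean / SD | share of true change | power |
|---|---|---|---|---|---|
| 0.3 | 0.404 − 0.0585 = 0.3455 | 0.987 | 0.350 | 86% | 63% |
| 0.5 | 0.404 − 0.0975 = 0.3065 | 0.963 | 0.318 | 76% | 55% |
| 0.8 | 0.404 − 0.1560 = 0.2480 | 0.903 | 0.275 | 61% | 44% |
| 1.0 | 0.404 − 0.1950 = 0.2090 | 0.844 | 0.248 | 52% | 37% |

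A simulation of 20,000 trials of 50 patients agrees: power 0.56, 0.44 and 0.38 at ρ = 0.5, 0.8 and 1.0.

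**4. Other shares unable, same formulas.** Cells show share of true change / power.

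| q | ρ = 0.3 | ρ = 0.5 | ρ = 0.8 | ρ = 1.0 | random loss (power) |
|---|---|---|---|---|---|
| 5% (n = 48) | 92% / 72% | 87% / 68% | 79% / 63% | 73% / 61% | 78.3% |
| 20% (n = 40) | 74% / 47% | 57% / 32% | 31% / 15% | 13% / 7% | 70.3% |

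The column ρ = 1.0 is a bound: it places every failure exactly on the largest decliners. Inability depends on the level reached, which is baseline plus change, so the true link should be weaker.

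**5. Keeping the failures.** In the same simulation, a signed-rank test with unable ranked worst had power of about 0.87, 0.79 and 0.79 at q = 10% and ρ = 0.5, 0.8 and 1.0. Over q = 5% to 20% and ρ = 0.5 to 1.0, it ran from about 0.78 to 0.94, against 0.68 down to 0.08 with blanks. Power on the stands-per-second scale was not computed.

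**The case against.** Several objections have force and limit the point.

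- **Silence is not exclusion.** A reader might infer that the plan drops these patients. It does not say so. A missing value is the default result of a seconds-only scale, and the choice is left until data are seen.
- **The decline is not hidden across the trial.** A reader might infer that it is. Five other measures can register severe weakness, and the AMAT item covers the same function. That item is summed with four other tasks, however, and does not repair the timed measure.
- **18 of 29 is not a failure rate.** Those patients needed some help, which is different from being unable to complete five stands. The Background says that probably only severe cases were referred. The figure (62%) shows that the event is plausible and supports no assumed share. This trial also enrols fitter patients and gives all of them exercise.
- **The paired t-test appears only in the power statement.** The optional repeated-measures or GEE model would keep a patient's earlier times. It would still have no value for the failed test, whose absence depends on the unobserved outcome, so the bias may be reduced but is not removed.
- **Overlap with drop-out.** Section VI already allows for loss, "if 10 (20%) out of 60 patients drop out early due to developing significant weakness", among other causes. Some patients who would fail the test may be among those 10, and removing a further share from the 50 could count them twice. The allowance does not cover patients who attend and fail.
- **This is a pilot meant to estimate.** Power on one test is then secondary. The bias in the estimate is the main harm, and it does not depend on testing.

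**Conclusion.** The point holds for one of the six primary measures. The timed sit-to-stand cannot record failure, and nothing elsewhere in the documents supplies a value. The direction, toward too little decline, follows whenever inability goes with worsening.

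Confidence is high for the missing rule and its direction, and much lower for size. At 10% unable the illustration runs from 86% down to 52% of the true change, the lower end being the worst case. It rests on an assumed share, an assumed correlation, a normal model that gives unable patients a notional finite time, and no overlap with the drop-out allowance. Most of the power lost comes from bias: random loss of the same number would cost about 4.5 points (80% to 75.5%), against 17 to 43 points here.

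This should be settled before any outcome data are examined.

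**What to change.** In Section V, item d, add a scoring line: record a failed attempt as unable because of weakness, with the number of stands completed, separately from a test not done for other reasons.

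In Section VI, pre-specify one analysis that keeps these patients. Two candidates:

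- stands per second, 5 divided by seconds, with unable = 0; or
- a signed-rank test on change with unable ranked worst.

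They target different quantities, so name one as the main analysis. Report the proportion unable at each visit, and time in seconds among those able as a descriptive companion.

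The cost is one scoring line and one or two analysis sentences, with no added visit, test or patient. The drawback is that a rate or rank is less familiar than seconds. The change does not recover patients who leave the study; that needs its own missing-data rule.
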